1.5.4 Pre-clinical survivin reactive IgG antibodies in human serum

In a consecutive series of 6 vaccine-naïve glioma patients, 5 had moderate titers of survivinreactive antibodies to whole recombinant survivin protein (see **Figure 6** below). Data indicate the possibility that previous immune exposure to survivin may naturally occur in GBM patients.

[figure not shown]

Figure 6: Serum ELISA for SVN53-67 reactive IgG antibodies in glioma patients who have not been vaccinated.

1.6 Safety Pharmacology

Peptides used for vaccination studies do not follow standard pharmacokinetics and such data are not likely to be useful to ascertain peptide safety. Previous studies of similar peptide designs have not shown any pharmacological effects upon vital functions. Consequently, pharmacological distribution studies of SurVaxM have not been performed.

Considering the route of administration (i.e., subcutaneous injection), it is very likely that SurVaxM will remain locally at the injection site for a long period and not be systemically available in any significant amount. Much of the peptide will be taken up by antigen presenting cells (APC) locally and then processed for presentation to the immune system. In addition, some fraction will be degraded locally by peptidases to produce clinically insignificant quantities of free amino acids and smaller peptides. Therefore, as with many other peptide vaccines tested to date, SurVaxM should not reach vital organs to directly affect them. Nonetheless every effort has been made to address the safety of SurVaxM through pre-clinical animal toxicity studies.

According to the study entitled "Subcutaneous Repeated Dose Toxicity Study of 012410-2 in C57BL/6 Mice with a Two-Week Recovery (Study No. 20003268)", subcutaneous administration of SurVaxM at a dose of 500 mcg in adjuvant Montanide ISA 51 VG injected with sargramostim every other week for 12 weeks was well tolerated by male and female mice throughout the dosage and recovery periods. Administration of SurVaxM did not cause mortality or adverse signs of toxicity as evaluated by clinical or skin reaction observations, changes in

body weights, ophthalmologic observations, necropsy observation, terminal body weights and organ weights, clinical pathology and histopathological observations.

1.7 Pharmacokinetics

The uptake of peptides used for vaccination studies is thought to be via phagocytosis by macrophages and dendritic cells, which do not follow established pharmacokinetic models. Absorption, distribution, metabolism and excretion of a 15 amino acid peptide and its composite naturally occurring amino acids cannot be confidently ascertained by standard methods. Upon administration, biological peptides essentially begin to be degraded to peptide fragments and amino acids masked by the systemic milieu. No formal pharmacokinetic studies have been conducted in either animals or humans since the drug is not systemically distributed upon administration.

1.8 Efficacy

1.8.1 Pre-clinical Data

1.8.1.1 SurVaxM in Syngeneic, Immunocompetent, Murine, Intracerebral Glioma Model

Beginning four days after tumor implantation, mice were immunized with either SVN53-67/M57 peptide-loaded dendritic cells or, by direct subcutaneous injection of 100 µg SVN53-67/M57-KLH peptide [in Incomplete Freund's Adjuvant (IFA)] plus 100 ng sargramostim. Vaccinations were repeated (boosted) every 7 days up to a total of 3 immunizations, and long-term survivors were confirmed to be tumor-free by MRI (**Figure 7**). SurVaxM produced enhanced survival in mice with GL261 cerebral gliomas with some survivors alive 1 year after implantation without detectable tumor. No significant difference was observed between survivin peptide-loaded DC or the peptide-KLH conjugate (SurVaxM), provided that sargramostim was used as a supporting adjuvant.

[figure not shown]

Figure 7: Survival of C57BL/6 mice bearing 1x10⁵ GL261 intracerebral gliomas. 1) Control DC: n=10, survival range 18-24 days, with median survival 19.5 days; 2) OVA: n=7, survival range 19-22 days, with median survival 21 days; 3) SVN53-67/M57 DC: n=14, survival range 40-120+ days, with median survival 55 days; 4) SVN53-67/M57 KLH: n=8, survival range 25-120+ days, with median survival 56.5 days. SVN53-67/M57-KLH or SVN53-67/M57 DC vs. control DC both p>0.0001.

1.8.1.2 SurVaxM with Temozolomide in Glioma-bearing C57BL/6 Mice

Mice with intracranial GL261 murine gliomas were treated with temozolomide 5 mg/kg/day for 10 days following tumor implantation. SurVaxM was administered as 100 ug peptide in Montanide with 100 ng sargramostim on day 12. Median survival for mice receiving combination of temozolomide and SurVaxM was 46 days, compared to 32 days for mice receiving SurVaxM alone. Significant differences were observed in terms of median survival but not overall survival. This study demonstrated that: 1) the combination of temozolomide and SurVaxM while not synergistic, was not detrimental to immunization response and had minimal toxicity and, 2) treatment with SurVaxM at a late stage (12 days post-implantation to accommodate temozolomide administration) was still effective (compared to initiation of vaccinations 4 days post-implantation in earlier studies, with much smaller tumor mass).

1.8.2 Clinical Data

The literature provides several immunotherapy trials that incorporate wild type survivin peptides as target antigens and show the induction of specific T-cell activity in a limited number of patients with advanced solid tumors (32-35). A phase II trial (36) in 61 HLA-A1/-A2/-B35-positive, metastatic melanoma patients, using survivin-targeted peptide vaccination demonstrated prolonged OS in 13/41 patients who exhibited survivin-specific T-cell reactivity (SSTR) (median 19.6 vs 8.6 months; p=0.0077). It also revealed that the induction of SSTR was associated with gender and disease stage, rather than age, HLA type, performance status or vaccination regimen. It was observed that the majority of treatment-related side effects were mild to moderate (CTC grade 1-2), including fever, chills on the day of vaccination and inflammatory reactions at the

injection sites. The occurrence of these post-vaccination inflammatory reactions was strongly associated with the presence of SSTR and a trend toward favorable survival.

SVN53-67/M57-KLH has been studied in a phase I clinical trial sponsored and conducted by Roswell Park Cancer Institute. In that trial, nine patients with recurrent, survivin-positive malignant gliomas who had failed standard therapy, received SVN53-67/M57-KLH [(500 mcg) in Montanide ISA 51 with sargramostim (100 mcg)] subcutaneously at two-week intervals, for four doses, until tumor progression. In addition, patients who survived six months or more without tumor progression, serious adverse events, or regimen limiting toxicity received maintenance phase dosing every three months. Toxicity attributable to SVN53-67/M57-KLH was mostly limited to mild injection site reactions. SVN53-67/M57-KLH-Montanide-sargramostim was well tolerated and the majority of AE were grade one. Six of nine patients experienced injection site reactions, all grade one, including localized areas of erythema related to vaccination. Three patients reported fatigue (grades 1 and 2), two patients experienced myalgias (grade 2). Lymphopenia was seen in 3 patients (all grade 1) and leukopenia (grades 1 and 2) occurred in three patients. The only grade 3 AE, a seizure, was not related to the vaccine. One SAE (renal failure) occurred in the maintenance phase in one patient but was unrelated to the study drug.

1.9 Risks and/or Benefits

1.9.1 SVN53-67/M57-KLH

Minor risks due to injection of SVN53-67/M57-KLH include:

- minor pain at the injection sites (common),
- local swelling of the subcutaneous tissues that may last several minutes to an hour (common)
- itching or redness at the injection site (common)
- infection is a possible risk of any injection (rare)

Major risks of SVN53-67/M57-KLH arise from the fact that although the survivin protein is rarely present in normal cells of the body, some normal cells could contain survivin making it possible that the vaccine could cause a reaction against normal tissues (autoimmunity). Patients will be observed for signs of such a reaction, using physical examinations and blood studies. A second major risk of treatment with SVN53-67/M57-KLH is that of a severe allergic or anaphylactic reaction. In the initial phase I clinical study, no allergic reactions or autoimmune phenomena were seen. All patients in this phase II study will be followed carefully for signs and symptoms of autoimmunity and allergic reactions.

1.9.2 Risks Associated with Montanide

SurVaxM (SVN53-67/M57-KLH) will be given together as an injection with Montanide ISA 51. Together these two agents will be injected just under the skin. Montanide helps to stimulate the immune system and keep the SurVaxM confined to the injection site so that it can work locally on the immune system. Montanide ISA 51 has been used extensively in clinical trials of vaccine

treatments and its risks are minor. These risks include: pain at the injection site, which can be treated with pain medicine; local skin irritation (swelling, local skin redness and sometimes itching) at the injection site; flu-like symptoms including muscle and joint aches.

Rarely, necrotizing granulomatous panniculitis with scarring and possible skin ulceration may occur as a result of subcutaneous injection of vaccines containing Montanide ISA 51. In suchy lesions, deep nodularity can occur at injection sites. High frequency ultrasound may be used to evaluate the injection sites of patients who complain of persistent tenderness or induration lasting over 4 weeks after injection to aid in the diagnosis.

If panniculitis is superficial it may affect the vascular supply to the epidermis leading to superficial skin ulceration. The risk of this complication may be minimized by ensuring that vaccine injection is not given too superficially. Patients that experience skin necrosis or ulceration may be treated with intralesional injection of Kenalog (1 ml lof 5 mg/ml solution) at the vaccine injection site approximately 4 weeks after vaccination. The injection site will be reassessed 4 weeks after Kenalog administration and further doses be modified based on clinically determined response. It is possible that intralesional Kenalog could attenuate the desired immunological response to vaccination. If skin ulceration occurs, secondary cellulitis in the area of ulceration is possible. In such cases, microbial culture and appropriate antibiotic therapy may be indicated.

1.9.3 Risks Associated with Sargramostim

Sargramostim is indicated for use in a limited number of clinical settings, including post hematopoietic stem cell transplantation; where the recommended dose (250 mcg/m² daily, for multiple days) far exceeds the dose used in the current trial of SurVaxM. Many of the side-effects of sargramostim have been seen when the drug has been injected into a vein, rather than subcutaneously. Overall, the risks of short-term treatment in our study with low dose sargramostim administered subcutaneously are expected to be low.

There is the possibility that patients vaccinated with SurVaxM and sargramostim could develop an immune response against the pharmaceutical sargramostim, potentially neutralizing it and rendering the patient unresponsive to future use of this drug. The risk of this occurrence is not defined, but there is very little risk of these patients subsequently developing a condition where sargramostim therapy would be appropriate since allogeneic stem cell transplantation is not a current standard therapy for patients with recurrent glioblastoma.

Minor Risks:

- o Tiredness and Headache. Headache can be treated with pain medicine.
- o Bone, joint and muscle pain. The doses at which these occur are generally higher than the dose used in this study.
- Skin rash and itching.
- o Local skin irritation (swelling, local skin redness and sometimes itching) may occur at the injection site.

- o Localized and widespread skin reactions are uncommon.
- Serious and potentially life-threatening allergic reactions with sargramostim are rare.
- o Fluid retention. This is usually reversible after sargramostim is stopped or drugs to reduce fluid retention are given.
- o High or low white blood cell or platelet counts.

Major Risks:

- o Pericarditis (irritation of the covering of the heart)
- o Pericardial effusion (fluid around the heart)
- Hypotension (low blood pressure) may occur as part of a "first-dose" reaction to sargramostim. This is much less common when sargramostim is injected under the skin, rather than into a vein. This reaction is accompanied by some or all of the following symptoms:
- Low blood pressure
- o Rapid heart beat
- Fainting
- o Fever
- Flushing
- Nausea
- Vomiting
- Sweating
- o Back pain
- Leg spasms
- Shortness of breath

Patients who have first-dose reactions may need treatment with fluids by vein and oxygen. Acetaminophen (Tylenol), Ibuprofen or narcotics (Lortab, Morphine or Dilaudid) may be given for pain relief. This reaction usually does not happen again with further doses of sargramostim during the same course of treatment.

- Abnormal heart beat (rare less than 1%). This is reversible when the medicine is stopped. It occurs more commonly in patients with a history of abnormal rapid heart beating.
- Poor kidney function has occurred in patients with previous kidney problems. Patients with kidney problems are not eligible for this study.

• Problems with liver function. While there have been no reports of severe liver problems, reversible increases in liver enzymes have occurred with sargramostim.

2 RATIONALE

Despite advances in surgery, radiation therapy and chemotherapy, including establishment of concurrent radiation and temozolomide followed by temozolomide as standard of care, glioblastoma (GBM) remains an incurable disease with a dismal median overall survival of less than 15 months⁽¹⁾.

This phase II study in patients with newly diagnosed glioblastoma follows a completed phase I study of patients with recurrent malignant glioma who had failed standard treatment, including temozolomide. In that study, all patients had received extensive treatment with temozolomide prior to receiving SVN53-67/M57-KLH with Montanide and GM-CSF.

There is a strong rationale for moving vaccine-based cancer therapy to the upfront setting in which a patient's immune system is best able to respond to the treatment. Numerous studies have shown that patients with glioblastoma have severe immunosuppression that improves significantly following surgical tumor resection. Tumor-mediated immunosuppression returns when the tumor recurs following failure of standard therapy. Therefore, vaccine-based therapy given soon after initial surgical resection stands the best chance of improving time to tumor progression and overall survival for GBM patients. In addition, studies of one other KLH-conjugated peptide vaccine (CDX-110; rindopepimut) to treat glioblastoma, Sampson et al. (37) showed that temozolomide-induced leukopenia is associated with an enhanced immunologic response to that vaccine. The mechanism for this is unclear, although it may involve differential susceptibility of certain immunomodulatory cells to temozolomide.

The rationale for proceeding directly to a phase II study is based on the following four points. First, the completed phase I trial of SVN53-67/M57-KLH showed very little toxicity with no grade III or IV adverse events and no serious adverse events attributable to the study drug. Second, there is no scientific rationale to posit additive or synergistic toxicity between the two drugs, given that temozolomide is an alkylating agent and SVN53-67/M57-KLH is a peptide vaccine. Third, in three separate GBM trials (ACTIVATE⁽³⁸⁾, ACT II⁽³⁹⁾ and ACT III⁽³⁷⁾), rindopepimut vaccine given in combination with temozolomide showed no serious toxicity with only minor injection site reactions, similar to expectations for SVN53-67/M57-KLH. Fourth, in addition to evaluation of immune responses and PFS, the current phase II design includes rigorous evaluation of toxicity of each drug with CTCAEv4.0 (see Sections 6.2.1 and 6.2.2).

3 OBJECTIVES

3.1 Primary Objective

To evaluate 6-month progression-free survival (PFS6) in patients with survivin positive newly diagnosed glioblastoma multiforme (GBM) treated with at least 4 doses of SurVaxM and standard of care temozolomide. PFS6 is defined as the percentage of patients without tumor progression or death from any cause 6 months after the date of diagnosis by biopsy.

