4 METHODOLOGY

4.1 Study Design

This is a multi-center, open label, single arm, phase II trial in adult patients with newly diagnosed GBM, evaluating the efficacy and safety of SurVaxM and adjuvant temozolomide after patients have received concurrent radiation and temozolomide.

Patients will receive a postoperative MRI, within 96 hours of surgical resection, followed by ~4 weeks recovery time. Then they will receive 6-week duration of radiation therapy with temozolomide. A post-chemoradiation MRI will be performed within 1-28 days to ensure no tumor recurrence or progression.

Figure 8 Pre-Study Treatment and Imaging Requirements

[figure not shown]

HLA tests and tumor testing for survivin status can be performed at any time prior to vaccine priming, while the rest of screening assessments should be performed after completion of chemoradiation and prior to vaccine priming.

As shown in **Figure 8**, first priming administration of SurVaxM should occur within 7-28 days after completion of chemoradiation. Adjuvant temozolomide therapy (TMZ) will begin \geq 28 days after completion of concomitant temozolomide radiation therapy and given for 6 cycles or more (at the discretion of the investigator), or until intolerance or tumor progression.

Figure 8 Treatment Schema

SurVaxM should be administered approximately every 2 weeks (\pm 3 days) during the priming phase and then approximately every 12 weeks (\pm 2 weeks) during the adjuvant phase. Following completion or discontinuation of TMZ in the absence of progression, SurVaxM may be continued approximately every 12 weeks during the maintenance phase until intolerance or disease progression.

All participants will sign an informed consent prior to study related tests. All participants will meet the inclusion and exclusion criteria summarized in **Section 5.1** and **Section 5.2** Participants will be treated on an outpatient basis.

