5 PARTICIPANT SELECTION

5.1 Inclusion Criteria

To be included in this study, participants must meet the following criteria:

- 1. Age \geq 18 years of age.
- 2. Have a Karnofsky performance status ≥ 70 (i.e. the patient must be able to care for himself/ herself with occasional help from others; refer to **Appendix B**).
- 3. Documented survivin-positive tumor status.
- 4. Pathologically confirmed diagnosis of glioblastoma multiforme (GBM). Or WHO grade IV [gliosarcoma]
- 5. Have the following clinical laboratory values obtained within 14 days prior to registration:
 - Absolute neutrophil count (ANC) $\geq 1.5 \times 10^9/L$
 - Platelets $> 100 \times 10^9/L$
 - Hemoglobin (Hgb) > 9.0 g/dL
 - Serum total bilirubin: $\leq 1.5 \text{ x ULN}$
 - ALT and AST < 4.0 x ULN
- 6. Patients on full-dose anticoagulants (e.g., warfarin or LMW heparin) must meet the following criteria:
 - No active bleeding or pathological condition that carries a high risk of bleeding (e.g., tumor involving major vessels or known varices)
- 7. Adequate renal function, as defined below:
 - Creatinine $\leq 1.8 \text{ mg/dl}$
- 8. HLA-A*02, HLA-A*03, HLA-A*11 or HLA-A*24 positive patients.
- 9. MRI (completed within 96 hours after surgery) documenting gross total resection consisting of no gadolinium enhancement; or subtotal resection consisting of linear enhancement with (or without) nodular gadolinium enhancement measuring no greater than 1 cm x 1 cm x 1 cm total volume or 100 mm² in cross sectional area.
- 10. No evidence of true progressive disease from the postoperative period to the post-chemoradiation period, based on changes in the neurologic exam, steroid use, or evident radiographic progression, according to RANO criteria (see **Appendix C**). Patients with increased or new gadolinium enhancement may continue on protocol if in the investigator's judgment that enhancement is likely due to pseuodoprogression. The use of correlative imaging studies (including PWI) or diffusion weighted imaging (DWI), and

- repeat imaging after an interval of 2-4 weeks is strongly encouraged to help distinguish between pseudoprogression and true progression.

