- 11. Participants of child-bearing potential must agree to use adequate contraceptive methods (e.g., hormonal or barrier method of birth control; abstinence) prior to study entry and, have a negative pregnancy test prior to starting study treatment. Should a woman become pregnant or suspect she is pregnant while she or her partner is participating in this study, she should inform her treating physician immediately.
- 12. Dexamethasone dose less than or equal to 4 mg daily at time of study enrollment.
- 13. Patients must have completed initial radiation therapy (RT) and temozolomide (TMZ) for the treatment of their glioblastoma (i.e., completed 6-week course of RT and, completed ≥ 75% of 6-week course of induction TMZ chemotherapy).
- 14. Participant or legal representative must understand the investigational nature of this study and sign an Independent Ethics Committee/Institutional Review Board approved written informed consent form prior to receiving any study related procedure.

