12 STATISTICAL METHODOLOGY

12.1 Study Design

This is a multi-center, open-label; prospective one-arm phase II clinical trial evaluating the safety and efficacy of SurVaxM and adjuvant temozolomide in adult patients with newly diagnosed GBM. The statistical design is based on an assessment of the efficacy of the study treatment for patients as compared to an external standard, i.e., historical control. All enrolled patients will receive the study treatment and initiation of the treatment should take place as soon as possible following study enrollment. A total of up to 65 patients will be enrolled to meet our target of at least 50 evaluable patients. An evaluable subject is defined as a subject who meets eligibility requirements and who completes the initial four priming doses of the vaccine. If a patient signs an Informed Consent and does not receive all four priming injections or, the patient withdraws their consent before receiving the priming injections, the patient will be classified as unevaluable and will be replaced. Analyses will be performed with a focus on estimation of specific clinically important parameters for use in the planning of larger subsequent comparative trials designed to fully assess efficacy and safety.

All analyses will be performed using the SAS® statistical software system.

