12.3 Study Endpoints

Primary Endpoint:

• PFS is defined as the time from date of diagnosis to the date of first observed disease progression or death due to any cause. All patients will be followed for a minimum of 6 months relative to evaluating the primary endpoint.

Secondary Endpoints:

- OS is defined as the time from date of diagnosis until date of death or the last date patient known alive (if death is not observed).
- Number of Grade 3 or 4 toxicities, according to National Cancer Institute Common Toxicity Criteria for Adverse Events (NCI CTCAEs) Version 4
- Immune responses to SurVaxM and predictors of response

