12.7 Efficacy Analysis

12.7.1 Primary Analysis

The primary objective is to evaluate the 6 month PFS survival fraction in patients with newly diagnosed GBM treated with at least 4 priming doses of SurVaxM and standard-of-care adjuvant

temozolomide as compared to historical control. PFS is defined as the time from date of diagnosis to the date of first observed disease progression or death due to any cause. Patients who are alive and disease free at the last study assessment will be treated as censored.

Historical Control: Patients in this population defined by the eligibility criteria receive standard-of-care which consists of concurrent temozolomide and radiation followed by adjuvant temozolomide. Based on provided historical information, the 6 month PFS survival fraction is assumed to be 0.55. We hypothesize that treatment with SurVaxM and adjuvant temozolomide will increase the 6 month PFS survival fraction to 0.70. Therefore the PFS survival fraction will be measured after all patients have been followed for 6 months.

The 6 month PFS survival fraction is estimated as standard binomial proportion. An exact one-sided binomial test will be used to test our primary hypothisis. The nominal significance level to be used for this test is 0.10. In addition, a Kaplan-Meier curve for PFS will be used calculated to generate summary descriptive statistics, e.g. median PFS.

Secondary Analyses

The estimated distributions of overall survival (OS), defined as the time from date of diagnosis to death due to any cause, will be obtained using the Kaplan-Meier method. Estimates of quantities such as median survival will be obtained. Corresponding confidence intervals will be computed. It is assumed *a priori* that any drop out times will be non-informative in terms of the censoring mechanism. Groups defined by levels of categorical or dichotomized numeric demographic/baseline variables will be compared in regards to time-to-event distributions using the log-rank test. Cox proportional hazards model regression will be utilized for multivariate analyses.

A summary of anticancer therapies received following the discontinuation of protocol therapy will be provided. Such therapies will be classified as chemotherapy, biological therapy, radiation, surgery, or other.

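### Patients who progress or die between vaccine doses 1 and 4 can leave the PFS6 test instead of counting as failures, and survival curves from diagnosis include pre-vaccine time largely free of possible events

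*Combined protocol and SAP*

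**What the plan says.** All references are to the combined protocol and SAP.

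- **Clock.** Section 3.1 defines PFS6 as the "percentage of patients without tumor progression or death from any cause 6 months after the date of diagnosis by biopsy". Section 12.3 says "PFS is defined as the time from date of diagnosis to the date of first observed disease progression" or death. OS has the same origin (12.3, 12.7.1).
- **Entry.** Section 5.1 requires "No evidence of true progressive disease from the postoperative period to the post-chemoradiation period" (item 10) and "Patients must have completed initial radiation therapy (RT) and temozolomide (TMZ) for the treatment of their glioblastoma" (item 13). Item 10 lets in new enhancement that the investigator judges to be pseudoprogression.
- **Timing.** Section 4.1 gives about 4 weeks of recovery after surgery and 6 weeks of chemoradiation, and then the "first priming administration of SurVaxM should occur within 7-28 days after completion of chemoradiation". Section 6.1 puts dose 4 on priming day 43.
- **Primary set.** Section 12.1: "An evaluable subject is defined as a subject who meets eligibility requirements and who completes the initial four priming doses of the vaccine". Sections 12.1 and 12.9 replace everyone else, up to 15 patients within a ceiling of 65.
- **Stopping vaccine.** Section 6.6 withdraws patients at RANO progression. Section 9.1 ends treatment for new enhancement during priming that is not thought to be pseudoprogression.
- **Null.** The historical-control paragraph of 12.7.1 begins "Patients in this population defined by the eligibility criteria receive standard-of-care" and continues "Based on provided historical information, the 6 month PFS survival fraction is assumed to be 0.55". The test is exact binomial, one-sided at 0.10. No source, time origin or progression-free condition is given for 0.55.
- **Use.** Section 12.1 intends the estimates for planning later comparative trials.

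**The concern.** In a single-arm trial the null rate is the control group, so it must describe the patients who are counted. Here membership of the primary set is settled about 17-20 weeks after diagnosis, and the event being counted can itself decide it. A patient who progresses after dose 2 is withdrawn, never reaches dose 4, becomes unevaluable and is replaced. Selection of that kind raises the observed PFS6 even if the vaccine does nothing. The comparison with 0.55 is the only efficacy test against a control.

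The second problem does not depend on the null. A Kaplan-Meier curve from diagnosis treats patients as at risk from day 0, although no one could be in the vaccinated cohort without first surviving to vaccination. The medians therefore include time that the vaccine could not affect. A later trial that randomises after chemoradiation and takes these medians as planning values would start from figures that are too long.

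**Working it through.** **1. Timeline** (sections 4.1 and 6.1; assumes diagnosis at surgery and 6 months = 26 weeks).

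- Dose 1: 4 + 6 + (1 to 4) = week 11 to 14, which is 11/26 = 42% to 14/26 = 54% of the window, or about 2.5 to 3.2 months.
- Dose 4 (day 43, so 6 weeks later): week 17 to 20, which is 65% to 77% of the window.

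A diagnostic biopsy before surgery would move both doses later on this clock.

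**2. The plan's own figure** (section 12.4: 0.55 against 0.70, one-sided 0.10, power 0.80). The cutoff is the smallest c with P(X ≥ c | n, 0.55) ≤ 0.10.

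- n = 49: c = 32, size 0.095, power 0.810. This is the smallest n that meets both targets.
- n = 50: c = 33, size 0.077, power 0.782.

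The stated 50 is one patient from the exact minimum. The sample-size arithmetic is not the problem. No cutoff is stated; 33 is the one the test implies.

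**3. Effect of removing failures between doses 1 and 4.** Suppose 0.55 is right for eligible patients counted from diagnosis, the vaccine has no effect, and a fraction g of vaccine starters fail before dose 4 and are replaced. Those removed are all failures, so the rate in the remaining set is 0.55/(1 − g). The false-positive rate is P(X ≥ 33 | 50, 0.55/(1 − g)).

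| g (assumed) | rate in four-dose set | false-positive rate |
|---|---|---|
| 0 | 0.550 | 0.077 |
| 2% | 0.561 | 0.10 |
| 5% | 0.579 | 0.15 |
| 10% | 0.611 | 0.29 |

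The nominal 0.10 is reached at a rate of 0.5604, which is g = 0.0186, or about 1 patient in 50. The documents give no value for g. Disease assessments are every 8 weeks ± 4 (Table 3) and priming lasts 6 weeks, so the first scan may fall before or after dose 4.

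**4. Event-free time in the curves.** Everyone who starts vaccine was alive at dose 1, so OS from diagnosis carries about 2.5-3.2 months in which death was impossible. In the four-dose set that stretch runs to week 17-20. The same holds for most PFS events. The exception is enhancement accepted as pseudoprogression and later back-dated to when it was first raised (9.2, 9.2.1), which can place an event before dose 1. The shift in the medians depends on hazards that the documents do not give, so none is calculated.

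**5. Power if 0.55 has to be replaced** (n = 50). The nulls below are 0.55/0.95, 0.55/0.90 and 0.55/0.80, as illustrations. Power depends on how 0.70 is carried over. One choice is a constant hazard ratio of ln 0.70/ln 0.55 = 0.60, so that the alternative is null^0.597. The other divides 0.70 by the same factor as 0.55.

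| null | cutoff | size | power, constant hazard ratio (alternative) | power, 0.70 rescaled (alternative) |
|---|---|---|---|---|
| 0.58 | 34 | 0.095 | 0.80 (0.722) | 0.86 (0.737) |
| 0.61 | 36 | 0.074 | 0.72 (0.745) | 0.87 (0.778) |
| 0.69 | 40 | 0.055 | 0.58 (0.800) | 0.96 (0.875) |

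The protocol states two proportions and no hazard ratio, so neither power column is the plan's own.

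**The case against.** The strongest defence is that 12.7.1 introduces 0.55 directly after describing patients who meet the eligibility criteria, and those criteria already include completed chemoradiation without true progression. On that reading the entry condition causes no inflation. This stands. A reader might infer that the test is inflated simply because patients must reach week 11-14 progression-free. That follows only if 0.55 is a from-diagnosis rate in unselected patients, which the documents do not show. The missing source is, by itself, a missing detail and not a demonstrated bias.

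The defence does not reach the four-dose condition. Completing four doses is not an eligibility criterion, so a rate for eligible patients is not a rate for four-dose completers.

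It can also be said that the four-dose population is openly declared in 3.1 and 12.7.1, so it is a chosen target and not an oversight. That is fair, although 12.2 states the primary objective without it. Declaring the condition does not give it a matching null.

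Third, few patients may be removed. Scans during priming may be sparse, suspected pseudoprogression stays on treatment, and back-dated progression still counts as failure. All true, and the reason the shares in step 3 are labelled as assumptions. For the same reason a reader should not lean on 33/65 = 0.51, the rate if all 15 replaced patients had failed. Replacement also covers withdrawal of consent, including before treatment, so that is only an outer bound.

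Finally, the medians are descriptive and their origin is stated. That limits the harm but does not remove it, given their intended use in planning.

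**Conclusion.** The concern holds in two parts, both following from the plan as written.

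- **Primary set.** Progressions and deaths between doses 1 and 4 can be replaced instead of counted, and 0.55 is not matched to the set that remains. There is little slack: removing about 2% of no-effect patients uses up the gap between the actual size of 0.077 and the nominal 0.10, and 10% would give 0.29. How far this happens in practice is unknown.
- **Survival curves.** OS from diagnosis, and largely PFS, includes about 2.5-3.2 months of pre-vaccine time in which the event could not occur. This rests on the protocol's own schedule and on diagnosis at surgery.

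Inflation of the PFS6 test from the entry criteria is possible but not shown. It should be settled by stating what 0.55 refers to.

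**What to change.** 1. **Primary set.** Make it all eligible patients who receive at least one vaccine dose. Count progression or death during priming as failure, and report the four-dose set as supportive. Recompute the cutoff at the number actually analysed; with 65 patients it would be 42 (size 0.075). Section 8.1.4 follows patients off treatment for survival only, so state how 6-month status is obtained, or classified, for those who stop vaccine early without progression.
2. **Curves.** Estimate PFS and OS from first dose, or from diagnosis with delayed entry at first dose, in all who start vaccine. Label the unadjusted diagnosis-based curves as descriptive.
3. **Null.** Confirm that 0.55 is a from-diagnosis rate in patients progression-free after chemoradiation. If it is not, replace it with S(6 months)/S(first dose) from a named source and recompute the cutoff and power. If no such source exists, report PFS6 with an exact confidence interval and make no superiority claim.

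**Cost.** If 0.55 is already matched, item 3 takes a sentence or two. Items 1 and 2 are wording and analysis changes using diagnosis and dose dates the study already needs; the diagnosis clock for PFS6 and its readout date do not move. Observed PFS6 may be slightly lower. First-dose medians are not directly comparable with diagnosis-based ones, and delayed-entry curves are unstable early, while few patients are at risk. Power under a new null could fall or rise (step 5 of the working), so the plan should say how it rescales 0.70 before quoting a figure.
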